#### **4.2.3.1 Coding of Adverse Event Terms**

The AE term (Investigator term) will be assigned to the lowest level term (LLT), and a preferred term (PT) will be classified by a high-level term (HLT), a high-level group term (HLGT) and a system organ class (SOC) according to the Medical Dictionary for Regulatory Activities (MedDRA) thesaurus, Version 25.0.

Although there can be multiple SOCs for a PT, each PT will be linked with one SOC, namely the primary SOC which is automatically assigned by MedDRA via one HLT, HLGt route.

The following coding data will be presented:

- LLT (Investigator term)
- PT
- Coding data per primary SOC:
  - HLT
  - HLGt

If no coding information is available for a specific AE, the AE will be presented as an 'Uncodable Event' in all summary tables.

AEs will be reported on a per-subject basis and per-event. On a per-subject basis this means that even if a subject reported the same event repeatedly (i.e., events mapped to the same PT) during the study period, the event will be counted only once. In the latter case the event will be assigned the worst intensity and the strongest relationship to the study medication. The earliest date will be regarded as start date of the event and the latest date/time will be regarded as stop date of the event within the assigned study period.

#### **4.2.4 Prostate Cancer Diagnosis**

Details of the underlying condition will be documented in the eCRF, including:

- Type of adenocarcinoma of the prostate
  - Hormone-sensitive Metastatic
  - Hormone-sensitive Non-metastatic
- Date of first diagnosis
- Presence of metastases (body region)
- Clinical signs and symptoms

---

Document:

C:\ProgramData\activePDF\Temp\DocConverter\API\Input\\$651f4dc0b253\$FE3041C5883446E892B20AB6D3F0E1BD.docx

Author: [name]

Version and Date: Version 1.0, 21 Apr 2023

Page 35 of 66

#### 4.2.4.1 TNM classification of prostate cancer

Table 9 presents the Primary Tumour, Lymph Node and Metastasis (TNM) classification of primary tumours.

**Table 9 TNM Classification of Primary Tumours**

Clinical (cT)	
TX	Primary tumour cannot be assessed
T0	No evidence of primary tumour
T1	Clinically inapparent tumour not palpable or visible by imaging
T1a	Tumour incidental histologic finding in ≤5% of tissue resected (at time of transurethral resection of the prostate [TURP])
T1b	Tumour incidental histologic finding in >5% of tissue resected (at time of TURP)
T1c	Tumour identified by needle biopsy (because of elevated prostate specific antigen [PSA] level)
T2	Tumour confined within prostate
Note: Tumours found in 1 or both lobes by needle biopsy but not palpable on digital rectal examination or reliably visible by imaging are classified as T1c)	
T2a	Tumour involves one-half of 1 lobe or less
T2b	Tumour involves more than one-half of 1 lobe but not both lobes
T2c	Tumour involves both lobes
T3	Tumour extends through the prostatic capsule
Note: Invasion into the prostatic apex, or into—but not beyond—the prostatic capsule is classified as T2	
T3a	Extracapsular extension (unilateral or bilateral)
T3b	Tumour invading seminal vesicle(s)
T4	Tumour fixed or invades adjacent structures other than seminal vesicles (e.g. bladder, levator muscles, and/or pelvic wall)

TNM= Primary Tumour, Lymph Node and Metastasis

Error! Reference source not found.10 presents TNM classification of regional lymph nodes.

**Table 10 TNM Classification of Regional Lymph Nodes (N)**

Clinical (cN)	
NX	Regional lymph nodes were not assessed
N0	No regional lymph node metastasis
N1	Metastasis in regional lymph node(s)

TNM= Primary Tumour, Lymph Node and Metastasis

Document:

C:\ProgramData\activePDF\Temp\DocConverter\API\Input\\$651f4dc0b253\$FE3041C5883446E892B20AB6D3F0E1BD.docx

Author: [name]

Version and Date: Version 1.0, 21 Apr 2023

Page 36 of 66

Table 11 presents TNM classification of distant metastasis.

**Table 11 TNM classification of distant metastasis (M)a**

Clinical (cM)	
M0	No distant metastasis
M1	Distant metastasis
M1a	Non-regional lymph nodes(s)
M1b	Bone(s)
M1c	Other site(s) with or without bone disease

TNM= Primary Tumor, Lymph Node and Metastasis

a If more than 1 site of metastasis is present, use the most advanced category

**4.2.4.2 Gleason Score**

The Gleason score is the grading system used to determine the aggressiveness of prostate cancer. Gleason grades range from 1 to 5 and describe how much the cancer from a biopsy looks like healthy tissue (lower score) or abnormal tissue (higher score). Most cancers score a grade 3 or higher.

Since prostate tumours are often made up of cancerous cells that have different grades, two grades are assigned for each participant. A primary grade is given to describe the cells that make up the largest area of the tumour and a secondary grade is given to describe the cells of the next largest area. These numerical values are added to calculate the Gleason score (see Table 12 and Figure 2).

For instance, if the Gleason score is written as 3 + 4 = 7, it means most of the tumour is Grade 3 and the next largest section of the tumour is Grade 4, together they make up the total Gleason score. If the cancer is almost entirely made up of cells with the same score, the grade for that area is counted twice to calculate the total Gleason score.

Typical Gleason scores range from 6–10 (**Error! Reference source not found.**). The higher the Gleason score, the more likely the cancer will grow and spread quickly. Each specimen is assigned 2 grades based on the most common and second most common pattern.

---

Document:

[figure not shown]
C:\ProgramData\activePDF\Temp\DocConverter\API\Input\\$651f4dc0b253\$FE3041C5883446E892B20AB6D3F0E1BD.docx

Author: [name]

Version and Date: Version 1.0, 21 Apr 2023

Page 37 of 66

Figure 2: Gleason score

Document:

C:\ProgramData\activePDF\Temp\DocConverter\API\Input\\$651f4dc0b253\$FE3041C5883446E892B20AB6D3F0E1BD.docx

Author: [name]

Version and Date: Version 1.0, 21 Apr 2023

Page 38 of 66

**Table 12 Gleason Scoring System**

Grade Group	Gleason Score	Gleason Pattern(s)
1	≤6	≤3 + 3
2	7	3 + 4
3	7	4 + 3
4	8	4 + 4 (3 + 5/5 + 3)
5	9 or 10	4 + 5, 5 + 4, 5 + 5

**4.2.5 Injection Site Inspection**

Each injection site will be visually inspected at each visit for local reactions such as pain, tenderness, erythema/redness and swelling. If the only reaction is induration, this should be indicated on the eCRF and reported as an AE. Any other local reactions will be graded according to the grades mentioned as specified in Table 13 and reported as an AE. Upon complete resolution of an injection site reaction, injection site inspections of that injection site can cease.

During the first administration of the injection, an injection site inspection (ISI) will be performed to ensure that the injection site is free from blemishes, tattoos, or other marks that may make subsequent ISIs difficult. ISIs will also be performed at 30 minutes, 4, 12- and 24-hours post-dose. The ISI will be performed at 30 minutes post-dose for all other IMP administration. ISRs will be reported as AEs.

At maintenance dose visits ALL injection sites must be inspected unless an injection site reaction has fully resolved (including induration). For example, at Day 42 the following injection sites should be inspected: D0 SC; D0 IM; D42 SC. And at Day 84 the injection sites for D0 SC; D0 IM; D42 SC; D84 SC should be inspected. Only when an injection site reaction (including induration) has fully resolved can inspection of that injection site stop.

**Table 13 FDA Local Toxicity Scale**

Local Reaction to Injectable Product	Mild (Grade 1)	Moderate (Grade 2)	Severe (Grade 3)	Potentially Life-threatening (Grade 4)
Pain	Does not interfere with activity	Interferes with activity or repeated use of non-narcotic pain reliever	Prevents daily activity or repeated use of narcotic pain reliever	ER visit or hospitalisation
Tenderness	Mild pain to touch	Pain with movement	Significant pain at rest	ER visit or hospitalisation
Erythema/Redness a	2.5–5 cm	5.1–10 cm	>10 cm	Necrosis or exfoliative dermatitis
Swelling b	2.5–5 cm and does not interfere with activity	5.1–10 cm or interferes with activity	>10 cm or prevents daily activity	Necrosis

ER=Emergency room

a In addition to grading the measured local reaction at the greatest single diameter, the measurement should be recorded as a continuous variable.

b Swelling should be evaluated and graded using the functional scale as well as the actual measurement.

Document:

C:\ProgramData\activePDF\Temp\DocConverter\API\Input\\$651f4dc0b253\$FE3041C5883446E892B20AB6D3F0E1BD.docx

Author: [name]

Version and Date: Version 1.0, 21 Apr 2023

Page 39 of 66

**4.2.6 Clinical Laboratory Evaluations**

Fasted (>8 hours) blood samples for haematology and biochemistry tests, as well as a urine sample for urinalysis, will be collected for safety monitoring at screening, baseline, Day 28, all dosing visits of Stage 2 and the follow-up visit. For safety analysis, a blood volume of approximately 8 mL will be drawn per timepoint. Full details of blood volumes drawn during the study are documented in the Laboratory Manual.

All laboratory results are standardized to Système International (S.I) units.

An overview of measured parameters is given in Table 14.

**Table 14 Clinical Safety Laboratory Tests**

Haematology:	Biochemistry:
Haemoglobin (mmol/l)	Alkaline phosphatase (U/l)
Erythrocytes (10E12/l)	ASAT (U/l)
Leucocytes (10E9/l)	ALAT (U/l)
Thrombocytes (10E9/l)	GGT (U/l)
Neutrophils (%)	Creatinine (μmol/l)
Eosinophils (%)	Fasting glucose (mmol/L)
Basophils (%)	Fasting insulin (mIU/l)
Lymphocytes (%)	Urea (mmol/l)
Monocytes (%)	Total Bilirubin (μmol/l)
Urinalysis:	Total protein (g/L)
Leucocytes (HPF)	Sodium (mmol/l)
Erythrocytes (HPF)	Potassium (mmol/l)
Epithelial cells (LPF)	Total cholesterol (mmol)
pH	LDL (mmol/l)
Protein (g/L)	HDL (mmol/l)
Glucose (mmol/L)	VLDL (mmol/l)
Urobilinogen (mmol/L)	Triglycerides (mmol/l)
Ketones (mg/dL)	HbA1c (screening visit only)
Bilirubin (mmol/L)	
Nitrite: positive or negative (presence or absence)	
Specific density (g/L)	

ALAT=alanine aminotransferase; ASAT=aspartate aminotransferase; HDL=high-density lipoprotein; LDL=low-density lipoprotein; VLDL=very low-density lipoprotein; GGT=gamma-glutamyl transpeptidase; HbA1c= glycated haemoglobin

In case a re-test is conducted for any of the quantitative and qualitative laboratory parameters during any visit, the results of the re-test will be utilized. Quantitative test results at each visit will be categorised by the laboratory as 'Normal' (within the reference range) or 'Abnormal' (outside the reference range) according to the subjects' individual reference ranges provided by the analysing laboratory. Abnormal results will be further classified as being 'Low' or 'High' depending on whether the result is below or above the reference range limits. For all abnormal values, clinical significance (as determined by the Investigator) should be indicated.

---

Document:

C:\ProgramData\activePDF\Temp\DocConverter\API\Input\\$651f4dc0b253\$FE3041C5883446E892B20AB6D3F0E1BD.docx

Author: [name]

Version and Date: Version 1.0, 21 Apr 2023

Page 40 of 66

Based on the normal ranges supplied by the lab and noted in Attachment 2, markedly 'Abnormal Low' or 'High' laboratory test results will be identified at each visit.

For the qualitative laboratory parameters (urinalysis, etc.), the presence or absence ('Present' or 'Absent') of each parameter will be recorded.

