3.2 Discussion of Study Design

Teverelix is currently being developed for chemical castration in participants with advanced prostate cancer. Five previous Phase 1 clinical studies of teverelix have been conducted in healthy male volunteers as well as 5 Phase 2 clinical studies in prostate cancer patients. In these studies, teverelix TFA depot formulation has been tested following administration by single and multiple (2) SC injection(s) at doses of 10 mg, 30 mg, 60 mg, 120 mg or 180 mg. Teverelix produced a rapid, marked suppression of serum levels of LH, T and, to a lesser extent, FSH. The teverelix TFA-induced hormone suppression demonstrated in these studies was fully reversible within 1 week and exhibited no signs of a weight effect. Overall, teverelix TFA was safe and well tolerated.

Three Phase 2 studies in participants with BPH have been conducted as well. In participants with BPH, a statistically significant decrease was observed in prostatic symptoms as early as 2 weeks after administration of teverelix TFA. Symptomatic improvement increased over time and was most pronounced at study completion (after 16 weeks). A total of 76% of participants on teverelix TFA were classified as responders.

For participants with APC suppression of T below castration level, this was achieved within 3 days and was maintained for 4 to 8 weeks. Teverelix TFA was also shown to rapidly reduce and normalise PSA levels. In the Phase 1 and 2 studies a small number of study subjects (0.6 to 1.5%) experienced transient elevated liver function enzymes. Standard monitoring of liver function enzymes is recommended for future clinical studies.

PK and PD data from 2 different studies indicate that the SC route of administration of teverelix TFA produces a more sustained suppression of T levels than the IM route. This appears to be due to the fact that the SC route is more effective at maintaining adequate systemic levels of teverelix TFA.

In this study, teverelix TFA is being tested in participants with APC with a loading dose regimen administered as 2 doses of 120 mg each, given IM and SC, followed by SC injections of 120 mg of teverelix TFA every 6 weeks thereafter, as the preferred treatment regimen. If this treatment schedule fails to induce castration levels of T (≤2 ng/mL), an

Page 34 of 84

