6.3.7 Adverse Events

All AEs, including intercurrent illnesses or pathological changes in laboratory values, must be reported and documented in detail including the time of start and end of onset and the outcome. The measures taken will be documented in the eCRF as well as intensity, relationship to study medication and seriousness of the AE.

6.3.7.1 **Definition of Adverse Events**

An AE is any untoward medical occurrence in a participant or clinical investigation participant who is administered a pharmaceutical product. This untoward medical occurrence does not necessarily have a causal relationship with the administered treatment. An AE can, therefore, be defined as any unfavourable and unintended sign (including abnormal laboratory findings), symptom, or disease that is temporally associated with the use of a medicinal (investigational) product, whether or not related to that medicinal (investigational) product. If, during treatment with an investigational product, pathological laboratory values occur which were not present before the treatment started, further clinical or laboratory tests must be

carried out until the values return to the normal range or until a plausible explanation is found (e.g. concomitant disease) for the change in the laboratory values.

Symptoms or clinically significant laboratory or instrumental (e.g. electrocardiographic) abnormalities of a pre-existing condition, such as cancer or other diseases, should not be considered an AE. However, occurrence of new symptoms, laboratory, or instrumental abnormalities, as well as worsening of pre-existing ones, are considered AEs.

Laboratory values outside the normal laboratory-specific reference range, which make an intervention necessary and/or are considered clinically significant by the investigator must be reported as AEs. If the abnormal laboratory value is a sign of a disease, only this diagnosis should be reported as an AE.

An AE is considered to be an adverse drug reaction (ADR) if a causal relationship between a medicinal product and an AE is at least a reasonable possibility.

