8.1.5 Analysis of Safety Data

Safety Endpoints

1. Number of participants with treatment-emergent AEs (defined as any AE occurring or worsening following treatment), summarised by system organ class (SOC) and preferred term (PT)

Note: Occurrence of ISRs will be included.

- 2. Mean changes in vital signs, triplicate 12-lead ECGs and laboratory data parameters at each visit during the 168-day treatment period, compared to baseline
- 3. Continuous 24 hour 12-lead Holter ECG (subset of 30 Group 2 subjects only)
- 4. Percentage of participants with ISRs at each visit during the 168-day treatment period *Note:* Photography of injections sites with visible injection site reactions will be performed at each visit, and ISRs will be scored based on a specific scoring matrix

The treatment-emergent AEs (defined as any AE occurring or worsening with the same date or later than that of the first application of study treatment) will be coded using the most recent version of the Medical Dictionary for Regulatory Activities (MedDRA) available at the study start date. This version will be used throughout the entire study. Updates to MedDRA will not be applied afterwards. Frequency tables for the preferred terms will be compiled based on participants experiencing an AE and on the number of AEs. These frequency tables will take the SOC into consideration.

All reported AEs will be listed and ISRs will be summarised.

The vital sign, triplicate 12-lead ECG, and laboratory data parameters will be presented using descriptive statistics and shift-tables with respect to normal ranges for each visit including changes from baseline.

Concomitant diseases and medical history will also be coded using MedDRA. These data will be presented using frequency tables by SOC and PT.

Previous medication and concomitant medication will be coded using the Anatomical Therapeutic Chemical Classification (ATC) dictionary. Frequency tables will be compiled based on the coding for the medication.

8.1.6 **Missing Data**

Missing efficacy data will not be replaced in general.

If a laboratory reports concentrations as unquantifiable (too low), the value will be set to 0. Values for samples that are not technically evaluable will be set to missing.

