#### 5.3.2 Other Endpoints

##### 5.3.2.1 Laboratory Data

If a laboratory reports a concentration as unquantifiable (too low), they will set the value to 0. If a laboratory reports a concentration as unquantifiable (too high), they will set the value to the upper limit for that value. Values for samples that are not technically evaluable will be set to missing by the laboratory.

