**6.9.3 Clinical Laboratory Parameters**

Clinical Laboratory Parameters include collected and derived quantitative and qualitative parameters. Parameters will be grouped by category (see Table 14 in Section 4.2.6). Qualitative parameters will be summarised by absolute counts (n) and percentages (%). Percentages will be based on the number of subjects with data.

Haematology and Biochemistry will have separate tables for Summary, Shift for normal ranges and shift for qualitative measures.

Urinalysis parameters will be summarised.

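### SAP 4.2.6 lets a re-test replace a valid safety laboratory result, so a genuine post-dose abnormality can drop out of the by-visit laboratory tables

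*SAP*

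**What the plan says.** SAP 4.2.6, in the text after its Table 14, states that where "a re-test is conducted for any of the quantitative and qualitative laboratory parameters during any visit, the results of the re-test will be utilized". The rule names no reason for the re-test and does not say which of several re-tests counts. Nor does it say whether a later or unscheduled sample is a re-test of the earlier visit. The same section then classes each visit's result as normal, low or high, and says that markedly abnormal "laboratory test results will be identified at each visit".

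For outputs, SAP 6.9.3 says "Haematology and Biochemistry will have separate tables for Summary, Shift for normal ranges and shift for qualitative measures". Protocol 8.1.5 plans descriptive statistics and "shift-tables with respect to normal ranges for each visit including changes from baseline", and lists mean laboratory change at each visit as a safety endpoint. It contains no re-test rule, and SAP 7.1 does not list one among the changes from the protocol.

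Protocol 6.3.7.1 says that when pathological laboratory values appear on treatment that were absent before, further clinical or laboratory tests must be "carried out until the values return to the normal range or until a plausible explanation is found".

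Invalid samples have their own rule in SAP 5.3.2.1: "Values for samples that are not technically evaluable will be set to missing by the laboratory".

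**The concern.** Re-tests are not a random sample of laboratory results. Under Protocol 6.3.7.1 they follow mainly from a new abnormal value. A rule that always keeps the re-test therefore replaces selected results, and the selected results are mostly abnormal ones. Some return towards normal on repeat, whether because the abnormality was short-lived or through ordinary regression to the mean.

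The first value may be perfectly valid. If it is replaced, the by-visit mean, the shift category and the marked-abnormality flag all describe the repeat. These are the outputs that do not depend on an investigator's judgement of clinical significance. The protocol has a named interest here: Section 3.2 reports that 0.6 to 1.5% of subjects in the Phase 1 and 2 studies "experienced transient elevated liver function enzymes" and recommends liver enzyme monitoring. A transient finding is the kind most likely to look normal on a repeat.

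**Working it through.** The plan states no figure for this rule, so there is nothing to reproduce. The check sets the provisions side by side and then considers scale.

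**1. Does the rule reach valid results?** Yes. It applies to any parameter at any visit and gives no condition on the first sample.

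**2. Are repeats prompted by abnormality?** Mainly. Protocol 6.3.7.1 makes follow-up of new pathological values mandatory, ending at normalisation or at a plausible explanation. The follow-up may be clinical and need not repeat the same assay.

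**3. Can a repeat fall under the same visit?** Yes, if taken soon. SAP Table 19 gives ±3 days at Days 28, 42, 84, 126 and 168, the Stage 2 visits with safety laboratory tests. For Day 84 the window is 84 − 3 = 81 to 84 + 3 = 87. Take a valid raised liver enzyme on Day 84 and a normal repeat on Day 86:

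| | Day 84 value used | Shift from a normal baseline |
|---|---|---|
| SAP 4.2.6 as written, repeat treated as the re-test | Day 86, normal | normal to normal |
| Scheduled valid result kept | Day 84, raised | normal to high |

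A repeat on Day 95 lies outside the window. Whether it could still count as the Day 84 re-test is not stated.

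**4. Does another planned table protect the first value?** The SAP text names none; Section 6.9.3 has no worst post-baseline output. The output shells are a separate attachment that is not in the documents.

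**5. What survives elsewhere?** Protocol 8.1.8 lists all recorded data. Protocol 6.3.7.1 makes an out-of-range value an adverse event if it needs intervention or is judged clinically significant. Under Protocol 6.3.7.2 a laboratory adverse event starts at the first sample showing the change, and a later normal sample only ends it.

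**6. Scale (context only).** Inputs are p = 0.006 to 0.015 (Protocol 3.2) and n = 60 planned in Group 2 (Protocol 3.1).
- Expected elevations, n × p: 60 × 0.006 = 0.36; 60 × 0.015 = 0.90.
- Chance of at least one, 1 − (1 − p)^n: 1 − 0.994^60 = 0.303; 1 − 0.985^60 = 0.596.
- With the 50 evaluable men the plan aims for: 0.26 and 0.53.

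These figures count elevations, not cases lost. With numbers this small, one replaced value could change a table entry from 1/60 (1.7%) to 0/60.

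**7. Share lost.** Let q be the probability that a same-visit repeat of a true abnormality is normal. The documents do not give q. The expected share of re-tested abnormalities lost equals q, so assumed values of 25%, 50% and 75% lose 25%, 50% and 75%. Of three such abnormalities, 3 × (1 − q) = 2.25, 1.5 or 0.75 would remain on average. All are lost only if every repeat is normal.

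**The case against.** The strongest reply is that this is a missing detail in a descriptive, uncontrolled study with full listings and adverse event reporting. Several parts of it stand.

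- A reader might infer that abnormalities vanish from the report. They do not: the values remain in the listings, and those that are clinically significant or need intervention remain in the adverse event tables. What is exposed is mainly the remainder, in the by-visit outputs.
- A reader might infer that the protocol orders repeats until values are normal. It also allows follow-up to stop at a plausible explanation.
- A reader might infer that the rule can only hide abnormalities. A repeat can be worse than the first value. Pre-dose, replacing an abnormal value with a normal one can create a normal-to-abnormal shift later; SAP Section 4 in any case takes the last non-missing pre-dose value as baseline.
- Many repeats may replace nothing. Follow-up samples may come weeks later, and Protocol 6.3.6 generally keeps discretionary extra tests out of the database, though it is not clear that this covers the mandatory follow-up of Protocol 6.3.7.1.
- An instruction on re-tests is still needed for invalid samples. SAP 5.3.2.1 sets them to missing but does not bring in the repeat.

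These points narrow the consequence; they do not justify the rule. Adverse event capture rests on investigator judgement, which shift and marked-abnormality outputs are meant to supplement, and a listing does not correct a table. Nor is the plan merely silent: followed as written, it replaces valid results.

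**Conclusion.** The concern holds in a limited form. SAP 4.2.6 replaces valid post-dose safety laboratory results with repeats that are prompted mainly by abnormality, and the SAP text names no output that preserves the first value in tabulated form. A loss requires a repeat that is normal, held in the database and attributed to the same visit. The affected outputs are the by-visit summaries, shift tables and marked-abnormality flags.

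The effect is predominantly towards normal post-dose. Its size cannot be computed, because neither the re-test frequency nor the share normal on repeat is given. The 0.36 to 0.90 expected liver enzyme cases should not be read as cases lost: Protocol 3.2 gives neither a threshold nor a duration for those elevations, and a transient elevation need not be normal at a same-visit repeat. The point concerns safety reporting and leaves the primary endpoint untouched, but it should be corrected before the tables are produced.

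**What to change.** Reword SAP 4.2.6 as follows.

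- Use the valid scheduled result for by-visit summaries, change from baseline and by-visit shift tables. Let the re-test replace it only when the scheduled sample was not technically evaluable. State that baseline still follows the definition in SAP Section 4.
- State how multiple repeats and unscheduled samples are assigned, including those that fall inside a visit window.
- Add a worst post-baseline shift and marked-abnormality output using all valid post-dose results, including repeats and unscheduled samples. This should be an additional output: taking the worst value within each by-visit table would build in a selection of its own.

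The cost is SAP wording, a derivation flag and a little extra programming, with no new data. The downside is that abnormality counts may be somewhat higher, particularly in men tested more often; a footnote to the worst-value table should say so.
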